PARTNERS HUMAN RESEARCH COMMITTEE PROTOCOL SUMMARY

Answer all questions accurately and completely in order to provide the PHRC with the relevant information to assess the risk-benefit ratio for the study. Do not leave sections blank.

PRINCIPAL/OVERALL INVESTIGATOR

[name]

PROTOCOL TITLE

An online pilot study of Version 2 of the smoking cessation smartphone app "Smiling instead of Smoking" (SiS)

FUNDING

American Cancer Society

VERSION DATE

October 25, 2018

SPECIFIC AIMS

Concisely state the objectives of the study and the hypothesis being tested.

The overall goal of this pilot study is to solicit feedback from nondaily smokers looking for smoking cessation support online (n=270) about Version 2 of a smartphone app we designed to support smoking cessation. Feedback will be collected via passively collected smartphone app usage data, surveys and, in a sub-sample (n=20), online video-conference user feedback sessions. Results will be used to guide the design of Version 3.0 of the "Smiling Instead of Smoking" (SiS) smartphone app. Specifically, our aims are to:

- (1)Assess ease-of-use and helpfulness of the app, as rated by app users 6 weeks after their chosen smoking cessation date
- Test if within-person changes occur in theorized mechanisms of (2) behavior change as nondaily smokers undergo a SiS app assisted quit attempt
- Identify app features in need of improvement, as identified by (3) passively recorded app usage patterns, REDCap open-ended survey items, and, in a sub-sample, user feedback sessions (n=20)

BACKGROUND AND SIGNIFICANCE

Provide a brief paragraph summarizing prior experience important for understanding the proposed study and procedures.

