Briefly describe study design and anticipated enrollment, i.e., number of subjects to be enrolled by researchers study-wide and by Partners researchers. Provide a brief summary of the eligibility criteria (for example, age range, gender, medical condition). Include any local site restrictions, for example, "Enrollment at Partners will be limited to adults although the sponsor's protocol is open to both children and adults."

An estimated 270 participants will participate (i.e., sign consent) in this study based on the following eligibility criteria: (a) 18+ years of age, (b) smartphone ownership (c) current nondaily smoker, who smokes at least weekly, and no more than 25 out of the past 30 days (i.e., 71% of nondaily smokers), (d) has current quit intention (i.e., 65-74% of nondaily smokers), and (e) interested in helping us develop a smartphone app for smoking cessation. We will stop enrollment when n=90 participants have completed the primary endpoint of the study, which is the 6-week follow-up. Our study will be conducted entirely remotely and will require a screening process prior to enrolling participants on the app. Based on our experience in Study 1 (#2017P001106), we expect that 1/3 of participants who initially provide consent will pass the screening process and be retained for the 6-week follow-up. Thus, we are estimating that n=270 will be necessary to sign the initial consent for this study in order for n=90 to complete the primary endpoint of this study.

Briefly describe study procedures. Include any local site restrictions, for example, "Subjects enrolled at Partners will not participate in the pharmacokinetic portion of the study." Describe study endpoints.

Participation will last 6 months, where surveys will be administered prior to the quit day (online, as part of a screening test), and at 2-week, 6-week, 3-month, and 6-month follow-ups of the participant's chosen quit day (Figure 2). Participants will use the

[figure not shown]

Figure 2. Timeline of Your Study Participation

app for a strongly encouraged period of 7 weeks (1 week before, 6 weeks following the quit attempt), and optional continued use thereafter.

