Aim 2 (Within-person changes). To test if nondaily smokers utilizing SiS Version 2 experienced changes over time on constructs theorized to underlie smoking cessation, we will use the online survey data and fit one repeated measures mixed effects model per construct of interest (i.e., desire to smoke, mood, self-efficacy to quit/stay quit, motivation), where the construct will be the dependent variable, and time (0=baseline, 1=2-week, 2=6-week, 3=3-month, 4=6-month) will be the predictor. Correlations over time will be modeled with an unstructured covariance matrix. A contrast statement will be used to compare baseline versus follow-up. Given the explorative nature of this study, we will not correct for multiple testing.

Aim 3 (Identify app features in need of improvement). To identify features of the app that are in need of improvement, we will examine the passively generated app usage data as nondaily smokers enrolled in our study undergo their quit attempts, and will generate descriptive summary statistics on these usage data. To gain deeper insight, we will also conduct user feedback sessions with a randomly selected subsample of participants.

For studies involving treatment or diagnosis, provide information about standard of care at Partners (e.g., BWH, MGH) and indicate how the study procedures differ from standard care. Provide information on available alternative treatments, procedures, or methods of diagnosis.

Not applicable.

Describe how risks to subjects are minimized, for example, by using procedures which are consistent with sound research design and which do not unnecessarily expose subjects to risk or by using procedures already being performed on the subject for diagnostic or treatment purposes.

Risks are expected to be minimal, and include breach of confidentiality, subject discomfort form answering questions about smoking, and discomfort from quitting smoking (see below). We will minimize these risks by safeguarding electronic data capture by using HIPAA-compliant electronic data capture processes, assuring participants that they do not need to answer any questions they do not want to answer, and by providing information on how to manage smoking cessation.

Describe explicitly the methods for ensuring the safety of subjects. Provide objective criteria for removing a subject from the study, for example, objective criteria for worsening disease/lack of

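### Aim 2 handles missed follow-ups using only each construct's own earlier scores; adding app use and the other constructs as auxiliary variables could reduce dropout bias at little cost

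*Combined protocol and SAP*

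**What the plan says.** Planned Analyses, Aim 2, states that "we will use the online survey data and fit one repeated measures mixed effects model per construct of interest". The constructs are four ("i.e., desire to smoke, mood, self-efficacy to quit/stay quit, motivation"). In each model "time (0=baseline, 1=2-week, 2=6-week, 3=3-month, 4=6-month) will be the predictor", and "Correlations over time will be modeled with an unstructured covariance matrix". The estimate of interest is a single comparison: "A contrast statement will be used to compare baseline versus follow-up". The section mentions no covariates, auxiliary variables, imputation or missing-data sensitivity analysis, and does not discuss dropout.

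App use is a separate data stream. Specific Aims says "Feedback will be collected via passively collected smartphone app usage data, surveys", and the privacy sections say these data sit on study servers. Their only planned use is under Aim 3: "we will examine the passively generated app usage data as nondaily smokers enrolled in our study undergo their quit attempts", followed by descriptive statistics.

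On loss of participants, Research Design and Methods says "we expect that 1/3 of participants who initially provide consent will pass the screening process and be retained for the 6-week follow-up". The same section describes app use as strongly encouraged for seven weeks, ending six weeks after the quit day, and optional afterwards.

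**The concern.** A likelihood-based mixed model with unstructured covariance keeps people with partial follow-up. It gives unbiased means if, given the observed scores on the modelled construct, dropout is unrelated to the missing ones. With one model per construct, that condition must hold using one construct's history alone.

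It fails if something outside that history predicts both dropout and the missing scores. Disengagement after relapse is an obvious candidate. App use may track it, and because it is logged passively it should still be available when a survey is not returned. That a log exists for every app user is an inference from passive collection, not a statement in the protocol. The other constructs add less: a missed survey loses all four at that wave, so they help mainly through earlier waves and where single questions are skipped.

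There is no control arm in which similar dropout bias could cancel. Any bias goes straight into the baseline-to-follow-up contrast, and the four contrasts are the whole of Aim 2.

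**Working it through.** **1. The plan's own figure.** 90 completers ÷ (1/3) = 270 consents, which matches the protocol. The fraction combines passing screening with retention, so it gives no dropout rate among app users. If that rate by week 6 were 10%, 20% or 30% (assumed), then 90/0.9 = 100, 90/0.8 = 112.5 (113) or 90/0.7 = 128.6 (129) people would have to start the app. The plan states no effect size, power or bias figure for Aim 2.

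**2. Relapse-related dropout, by hand.** Assumptions, none from the documents: 60% relapse; relapsers score 0.5 to 0.8 SD worse at week 6; 10% of the others do not respond. For a simple mean of responders,

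bias = (0.60 − relapsers' share among responders) × score gap.

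- Relapser non-response 35%, gap 0.5: share = 0.39/(0.39 + 0.36) = 0.52; bias = 0.08 × 0.5 = 0.040 SD.
- 45%, gap 0.8: share = 0.33/(0.33 + 0.36) = 0.478; bias = 0.122 × 0.8 = 0.097 SD.
- 20%, gap 0.5: share = 0.48/(0.48 + 0.36) = 0.571; bias = 0.029 × 0.5 = 0.014 SD.
- 25%, gap 0.8: share = 0.45/(0.45 + 0.36) = 0.556; bias = 0.044 × 0.8 = 0.036 SD.

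**3. The same setting by simulation.** Maximum likelihood with unstructured covariance, three waves, retest correlation 0.5. Conditioning on the construct's own history lowers these figures only slightly.

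- Non-response 35–45% v 10% (overall 0.6 × 0.35 + 0.4 × 0.10 = 25% to 0.6 × 0.45 + 0.4 × 0.10 = 31%): bias 0.036–0.085 SD. Adding app use that correlates 0.5–0.7 with relapse leaves 0.018–0.064 SD.
- Non-response 20–25% v 10%: bias 0.012–0.032 SD, of which app use removes 0.003–0.015 SD.
- At 125 app starters with 35–45% v 10%: bias 0.044–0.093 SD against a sampling SD of 0.104–0.112. The largest ratio is about 0.093/0.104 = 0.9. Coverage of a nominal 95% interval is 0.875–0.928 without app use and 0.903–0.937 with it.

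**4. Varying the mechanism.** Five waves, SD 1, between-wave correlation 0.5, true change 0.30 SD, 200,000 simulated people per setting. App use correlates 0.3 or 0.5 with the part of the score not explained by its history. Week-6 bias in SD, planned model → with app use (correlation 0.3; 0.5):

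| Dropout driven by | 10% lost by week 6 | 20% | 30% |
|---|---|---|---|
| app use | 0.017→0.001; 0.028→0.002 | 0.031→0.000; 0.051→−0.001 | 0.047→−0.001; 0.078→−0.002 |
| app use and unseen score equally | 0.032→0.022; 0.041→0.022 | 0.077→0.057; 0.083→0.044 | 0.105→0.076; 0.123→0.065 |
| unseen score only | 0.054→0.050; 0.051→0.039 | 0.107→0.098; 0.101→0.076 | 0.157→0.144; 0.155→0.119 |

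Where app use drives dropout but is unrelated to the score, the planned model is already unbiased (−0.003 to 0.005) and nothing is gained.

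At 113 starters with 20% lost, app use driving dropout and correlation 0.5, the standard error of the average follow-up contrast is 0.080 without and 0.079 with app use. The large-sample bias in that average is 0.055, and 0.055/0.080 = 0.7 standard errors.

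**5. The full auxiliary set at pilot size.** Assumptions: 125 starters, 4 × 5 = 20 construct scores plus three app-use variables, five waves, 40% v 10% non-response by week 6. Week-6 bias fell from 0.059 to 0.024 SD, a cut of 0.035/0.059 = 59%. Month-6 bias fell from 0.082 to 0.036 SD, a cut of 0.046/0.082 = 56%. Sampling SD was essentially unchanged, and the analysis did no harm when app use was uninformative.

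**The case against.** The planned model is a standard choice, and auxiliary variables are a refinement. The study's stated primary goal is qualitative input, Aim 2 is called exploratory, and there is no power target or decision threshold. Follow-up surveys are paid ($25 each, $50 at week 6), which may keep non-response low. The avoidable part of the bias can be small: in the milder relapse setting app use removes at most 0.015 SD. All of this stands, and it is why the point is an improvement and not a defect.

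A worry that some 23 auxiliary variables would be unstable in about 125 people does not stand, given step 5.

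Three stronger readings are tempting but unsupported.

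- **That the contrasts are biased.** This needs app use or the other constructs to predict both dropout and the missing scores beyond the construct's own history, and no section says so. The protocol's theory (exercises raise positive affect and confidence and lower craving) makes a link to the scores plausible but says nothing about dropout. Even the direction is open, since someone who has quit may stop needing the app.
- **That the design expects heavy dropout.** The one-third figure includes screening failure, and screening comes before people are put on the app.
- **That the contrasts set parameters for the Study 3 RCT.** The protocol says that results in general guide Version 3 and that Study 3 will test that version. It goes no further.

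**Conclusion.** The point holds conditionally. Each Aim 2 model deals with missed follow-ups from one construct's own history, while information already being collected goes unused. If app use or the other constructs predict both dropout and the missing scores, the contrasts may be more biased than necessary.

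Under the assumed relapse settings the week-6 bias is about 0.01 to 0.09 SD, up to roughly one sampling SD at 125 starters. If dropout follows the unseen score itself, the assumed settings reach 0.16 SD at week 6, and app use then removes little. Across mechanisms the auxiliary data remove from none of the bias to nearly all of it. They should help most at weeks 2 and 6, because low use after week 6 is a weaker sign of relapse. The month-6 gain in step 5 depends on its assumptions in the same way.

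All rates, correlations and score gaps are assumptions; the documents supply none of them. This is a cheap improvement.

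**What to change.** Keep the planned mixed model and baseline contrast, and add the following to Planned Analyses, Aim 2.

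1. For all participants who started the app, repeat each contrast using multiple imputation (for example 50 sets) or a joint likelihood model. Include as auxiliary variables the other three constructs at all waves and a few app-use summaries, such as days used to week 2, days used to week 6, and date of last use.
2. Report survey non-response at each wave by level of app use, so that readers can see whether the log carries information on dropout.
3. Add one table that shifts imputed values in the unfavourable direction (more desire to smoke, worse mood, lower self-efficacy and motivation) by 0 to 0.5 SD, and mark where each conclusion changes. This covers the bias that auxiliary data cannot remove, and matters most at 3 and 6 months.

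The cost is analysis wording, extra programming and possibly slightly wider intervals. No new data are needed and participants are not burdened.

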To address this need, we are in the process of developing a smartphone app that acts as a behavioral, in-the-pocket coach and uses positive psychology exercises to enhance guitting success. Treatment via smartphone app is promising given the demonstrated effectiveness of texting interventions. It is particularly appealing because it is anonymous, portable, and provides just-in-time support, an important feature for smokers who smoke under specific conditions and circumstances. To support treatment, we use a positive psychology approach. Positive affect enhancement is an empirically sound treatment target: positive affect is psychometrically and neurologically distinct from negative affect, and plays an important role in the days leading up to and following a guit attempt. Enhancing positive affect with brief, self-administered exercises is entirely feasible: in recent years, a large number of positive psychology exercises have been developed that have consistently led to improvements in happiness, reductions in depression, and improvements in overall well-being. The smartphone app administers such positive psychology exercises to enhance and/or maintain positive affect, which is hypothesized to stimulate nondaily smokers to enact healthier alternatives to smoking by broadening their thought-action repertoire, increasing confidence, and decreasing craving and defensiveness about smoking-related health information (Figure 1). The focus on happiness will help overcome treatment resistance, as the pursuit of happiness is generally appealing and non-stigmatizing. To this end, we have worked closely with nondaily smokers in Study 1 (#2017P001106) to develop Version 2 of our "Smiling Instead of Smoking" app. In the current study (i.e., Study 2 in a series of 3 studies funded by the American Cancer Society (130323-RSG-17-021-01-CPPB)), we will conduct a larger pilot study to gain feedback from nondaily smokers on Version 2. Study 3 will be a proof-of-concept RCT of Version 3 of this app.

[figure not shown]

Figure 1. Treatment mechanism.

RESEARCH DESIGN AND METHODS

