Potential Benefits: All participants will receive behavioral counseling and smoking cessation resource information as part of their study participation. They will also engage in positive psychology exercises designed to increase positive affect to support smoking cessation. Consequently, participants in this study may quit smoking as a result of their participation, which would have a positive impact on their health. Furthermore, study participation will provide generalizable knowledge about the process of smoking cessation in nondaily smokers, which can be used to guide the development of further treatments to support smoking cessation in this growing population of smokers.

EQUITABLE SELECTION OF SUBJECTS

The risks and benefits of the research must be fairly distributed among the populations that stand to benefit from it. No group of persons, for example, men, women, pregnant women, children, and minorities, should be categorically excluded from the research without a good scientific or

ethical reason to do so. Please provide the basis for concluding that the study population is representative of the population that stands to potentially benefit from this research.

We are limiting study participation to persons who own a smartphone, because only such persons could benefit from the intervention. The criterion for having a current quit intention is necessary, because we will ask participants to quit as part of this study, and because the intended target audience of this treatment will be nondaily smokers who want to quit smoking.

No studies that we are aware of describe sex differences in the prevalence of intermittent smoking. Thus, we expect to enroll and retain female and male participants at equal rates. We do, however, expect to recruit and enroll slightly more participants of ethnic or racial minority status than reflective of general population rates, because studies indicate that intermittent smoking is more prevalent among African Americans, Asians, American Indians, and Latinos than Whites. There are no foreseeable risks associated with the inclusion for women and minorities in the study.

When people who do not speak English are excluded from participation in the research, provide the scientific rationale for doing so. Individuals who do not speak English should not be denied participation in research simply because it is inconvenient to translate the consent form in different languages and to have an interpreter present.

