We will exclude people who do not speak English, because the app we are developing is currently only available in English. Moreover, several of the scales we will be administering in the online surveys are only available in English.

For guidance, refer to the following Partners policy:

Obtaining and Documenting Informed Consent of Subjects who do not Speak English https://partnershealthcare-public.sharepoint.com/ClinicalResearch/Non-English Speaking Subjects.1.10.pdf

RECRUITMENT PROCEDURES

Explain in detail the specific methodology that will be used to recruit subjects. Specifically address how, when, where and by whom subjects will be identified and approached about participation. Include any specific recruitment methods used to enhance recruitment of women and minorities.

We will use both commercial advertising (e.g., Facebook) and grass-root efforts (e.g., Craigslist, quit smoking forums). We will use stratified enrollment to ensure that our final sample will (a) be equally balanced between men and women, and (b) reflect national prevalence rates of

nondaily smoking in terms of ethnicity and race, where we will enroll no more than 54% non-Hispanic White participants, as per the 2014 National Health Interview Survey

(http://www.cdc.gov/nchs/nhis/nhis 2014 data release.htm), which shows that 54% of nondaily smokers are non-Hispanic White.

Provide details of remuneration, when applicable. Even when subjects may derive medical benefit from participation, it is often the case that extra hospital visits, meals at the hospital, parking fees or other inconveniences will result in additional out-of-pocket expenses related to study participation. Investigators may wish to consider providing reimbursement for such expenses when funding is available

Participants will be remunerated according to the following remuneration schedule:

Table 1. Remuneration Schedule

Visit	Phone Conversations	Surveys	
Enrollment	\$20	\$25*	
2-week		\$25*	
6-week	\$25	\$50*	
3-month		\$25*	
6-month		\$25*	
\$195	With Skype session		
\$170	Without Skype session		
	* \$10, if check items are answered incorrectly		

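### Does Aim 2 need to name its mood measure and say whether positive affect is scored apart from negative affect?

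*Combined protocol and SAP*

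**What the plan says.** The Aim 2 paragraph under Planned Analyses takes its data from the online surveys and fits "one repeated measures mixed effects model per construct of interest (i.e., desire to smoke, mood, self-efficacy to quit/stay quit, motivation". Time, with five survey occasions, is the predictor. The within-person covariance is unstructured, and a contrast compares baseline with follow-up. The outcomes are introduced as "constructs theorized to underlie smoking cessation". On multiplicity the paragraph says: "Given the explorative nature of this study, we will not correct for multiple testing".

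Three other places bear on mood:

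- Background and Significance: "Positive affect enhancement is an empirically sound treatment target", with the reason that "positive affect is psychometrically and neurologically distinct from negative affect". The app's exercises are meant to "enhance and/or maintain positive affect".
- Expected Benefits: participants do "positive psychology exercises designed to increase positive affect to support smoking cessation".
- Equitable Selection of Subjects: "several of the scales we will be administering in the online surveys are only available in English". This is the only mention of the survey instruments, and none is named.

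**The concern.** The protocol's theory gives positive affect a special role. It is what the exercises are meant to move, and it is said to be separate from negative affect. Aim 2 is meant to test change in the theorized mechanisms, yet the only entry that could carry positive affect is the single word mood, with no scale, subscale or direction of scoring.

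Two consequences seem possible. If mood is one combined score, the result cannot show whether positive affect itself moved, and a change confined to positive affect would be diluted. If the instrument gives two scores, the analyst might report whichever looks better, with no correction for multiple testing. Either way a reader of the results could not tell from the plan which mood analysis had been intended.

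**Working it through.** **The plan's own figure.** The only sample-size figure is the number consenting: 90 completers at 6 weeks, with one third of those consenting expected to get there, gives 90 / (1/3) = 270. It reproduces exactly and has no bearing on mood. The plan states no alpha, effect size, standard deviation or power, so everything numerical below rests on assumptions.

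**How many models are planned?** The Aim 2 text gives one model per construct, and its list is introduced by i.e., which makes it complete. Mood is one entry of four. The count is 4 models, with one mood outcome. A count of 5 arises only by carrying the affect distinction from the background section into the analysis text, which does not make it.

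**Is mood treated differently from the other constructs?** No. Desire to smoke, self-efficacy and motivation also have no named scale. Self-efficacy even has two parts on its face, quitting and staying quit. The background pathway also includes more confidence and less craving, which plausibly correspond to self-efficacy and desire to smoke. The mechanism is therefore not tested through mood alone.

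**What would picking the better of two scores cost?** Assume a two-sided 0.05 level (critical value 1.96) and correlation rho between the two test statistics. The chance that at least one is significant under no change is 1 - P(|Z1| < 1.96 and |Z2| < 1.96):

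| rho | chance |
|---|---|
| 0 | 1 - 0.95^2 = 0.0975 |
| -0.25 | 0.0959 |
| -0.5 | 0.0907 |

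A single fixed score gives 0.05.

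**Would two models lower that?** No. With positive and negative affect each modelled, neither designated as the mood result and no correction, the chance that at least one is nominally significant stays at 9.1% to 9.8%. Across Aim 2, with independent tests at 0.05, it rises from 1 - 0.95^4 = 0.185 to 1 - 0.95^5 = 0.226.

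**What would a composite cost?** Take n = 90, a change of 0.3 SD of the change score in positive affect only, and approximate power = Phi(d x sqrt(90) - 1.96).

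- Positive affect alone: 0.3 x 9.487 - 1.96 = 0.886, power 81%.
- Equally weighted positive-minus-negative composite with equal SDs: d becomes 0.3 / sqrt(2(1 - r)), where r is the correlation of the two change scores. At r = 0, d = 0.212 and power is 52%. At r = -0.5, d = 0.173 and power is 38%.

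The loss is real if such a composite is used. However, the effect size, the correlation and the composite itself are all assumed, and the plan mentions no composite.

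**The case for a change.** The strongest reply is that exploratory status explains the lack of a multiplicity correction but does not explain an undefined dependent variable. Aim 2 is a stated aim. Its model, covariance structure and contrast are written out, and the results feed the design of Version 3.0. Which score enters the model is an analysis decision, and a list of survey items would not settle it. The investigators know their instrument, so naming it would take a sentence or two.

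Part of this stands. The text supplied does not say which mood score is meant, and mood is where the omission is most noticeable, because the protocol itself separates the two kinds of affect. Nor does the mention of scales prove that scoring was settled in advance. The survey forms and the mechanism figure are not in the text available here, so it cannot be shown either that the choice was fixed or that it was left open.

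The rest does not carry. A missing name is not a wrong rule: nothing in the Aim 2 paragraph would produce an incorrect result if followed. No passage promises a separate test of positive affect, so nothing is contradicted. The case against the plan needs an analyst who selects after the fact, and the documents describe no such selection.

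**Conclusion.** This is a gap that analysts fill sensibly. The investigators had chosen scales, an analyst will score the mood scale in its standard way, and a report of Aim 2 would normally name the scale and score for each of the four constructs. The plain reading is four models with one mood outcome.

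The sizes are hypothetical. The 9.1% to 9.8% against 5% requires an assumed level, an assumed correlation and post-hoc selection. The drop in power from 81% to between 38% and 52% requires an assumed effect confined to positive affect and an assumed composite. Adding a fifth uncorrected model would leave the first figure where it is and raise the Aim 2 total from 18.5% to 22.6%.

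Little depends on the answer. The Sample size and Power Considerations section puts qualitative input first, Version 3.0 also draws on ratings, usage data and feedback sessions, and without a control group no change in mood can be credited to the app. The conclusion rests on reading the list of constructs as closed and on the absence of any decision rule tied to mood. Both can be checked in the text.

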Participants will complete two types of assessment: (1) surveys, and (2) (in a sub-sample) user feedback sessions conducted via Skype. Potential participants will click-through to the study website. This website will explain that participants must call study staff in order to be phone-screened and to participate in the study. During the phone-screen, participants will be directed to complete an online survey via REDCap. Within the survey, participants will be asked if they would be willing to participate in an online video-conference user feedback session after they have used the app for seven weeks (1 week pre, 6 weeks post their chosen smoking quit day). Participation in the user feedback session is optional. Participants will receive survey links for 2-week, 6-week, 3-month and 6-month follow-ups via an emailed link. If selected for the online user feedback sessions (selected at random from interested participants), participants will receive an email and/or phone call upon completing their 6-week survey to set up the user feedback session.

The online user feedback sessions (n=20) will consist of the participants, and 1-2 members of the study staff. Relatively little guidance will be provided in this setting. Instead, 4 open-ended questions will be posed (i.e., did the app help you in your quit attempt? What did you like? What did you dislike? How could the app be improved?). All conference calls will be video-recorded for later analysis.

Sample size and Power Considerations: The primary goal of this study is to gather qualitative input rather than data to detect a pre-specified effect. The goal of this pilot study is to get input from app users who are interacting with the app and study staff completely remotely, without the benefit of inperson interaction, which is closer to the real-world experience potential users would have than the participants in Study 1. Thus, to identify issues not identified within the smaller sample in Study 1, we tripled the sample size of the current study, Study 2.

Planned Analyses:

Partners Human Subjects Research Application Form Version Date: October 15, 2014

Aim 1 (Ease-of-use and usefulness). To assess the degree to which SiS Version 2 is easy to use and perceived as useful by nondaily smokers attempting to quit smoking, we will use the Week 6 survey data, and will calculate means and standard deviations for the survey items querying ease of use and usefulness for each feature of the app.

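### Does Aim 2's contrast of baseline with follow-up need a named visit, when an equal-weight average would draw half its weight from after the encouraged app-use period?

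*Combined protocol and SAP*

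**What the plan says.** Planned Analyses, Aim 2, will "fit one repeated measures mixed effects model per construct of interest" (desire to smoke, mood, self-efficacy, motivation), where "time (0=baseline, 1=2-week, 2=6-week, 3=3-month, 4=6-month) will be the predictor". The covariance over time is unstructured. The comparison is then given in one sentence: "A contrast statement will be used to compare baseline versus follow-up". On multiplicity the plan says: "Given the explorative nature of this study, we will not correct for multiple testing".

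Three other places bear on the point:

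- **Specific Aims, Aim 2:** the interest is in change as "nondaily smokers undergo a SiS app assisted quit attempt". Aim 1 in the same list is tied to 6 weeks after the quit date; Aim 2 has no time window.
- **Research Design and Methods, study procedures:** participants use the "app for a strongly encouraged period of 7 weeks (1 week before, 6 weeks following the quit attempt), and optional continued use thereafter".
- **Research Design and Methods, enrollment, and Planned Analyses, Aim 1:** "We will stop enrollment when n=90 participants have completed the primary endpoint of the study, which is the 6-week follow-up"; and for ease of use and usefulness, "we will use the Week 6 survey data".

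**The concern.** With four follow-ups, a comparison of baseline with follow-up does not define a single quantity. The simplest reading is one contrast per construct against the average of all four. Half of that average would come from surveys about 7 and 20 weeks after the strongly encouraged period ends.

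If a construct moved while people were using the app and then drifted back, the average would shrink the change. If it moved later, the average would exceed the change seen during app use. One pooled number would not separate these cases. The protocol also has an obvious anchor, the 6-week visit, which Aim 2 does not use.

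A second worry is that the plan makes no multiplicity correction. An analyst could choose between one contrast per construct (4 tests) and one per visit (16 tests) after seeing the data.

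**Working it through.** **Figure given in the plan.** Aim 2 has no stated effect, power or alpha. The only sample-size figure is the number consenting: 90 / (1/3) = 270, which reproduces. The concern does not depend on it.

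**Weights.** The equal-weight contrast on (baseline, 2-week, 6-week, 3-month, 6-month) is (-1, 1/4, 1/4, 1/4, 1/4). The share from the last two visits is 2 x 1/4 = 50%. Taking 3 and 6 months as 13 and 26 weeks, they fall 13 - 6 = 7 and 26 - 6 = 20 weeks after the encouraged period. The share is 0% for a 6-week contrast and 100% for a 6-month contrast, so the 50% belongs to one reading only.

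**Possible dilution.** Let the change be d at weeks 2 and 6 and r*d at 3 and 6 months. The value of r is an assumption; the documents give none. The contrast estimates (d + d + rd + rd)/4 = d(1 + r)/2.

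| r | -0.5 | 0 | 0.5 | 1 | 1.5 |
|---|---|---|---|---|---|
| pooled estimate | 0.25d | 0.5d | 0.75d | d | 1.25d |

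Each entry is a correct average change over the four surveys. It is wrong only if Aim 2 is limited to the first 7 weeks.

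**Is Aim 2 limited in that way?** Specific Aims gives it no window. Planned Analyses describes it as change over time and lists the 3- and 6-month surveys as levels of the predictor. One construct covers confidence in staying quit, which remains relevant after week 6. What ends at week 6 is strong encouragement, not app use. The statements about week 6 concern Aim 1 and the enrollment stop, and neither is linked to the Aim 2 contrast.

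**Precision cost of a 6-week headline.** Assume equal variances and equal numbers at each visit. With within-person correlation 0.5 between all visits (compound symmetry):

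- 6-week minus baseline: variance 2(1 - 0.5) = 1.
- Four-visit average minus baseline: 1 + (1 + 3 x 0.5)/4 - 2 x 0.5 = 0.625.
- Ratio of standard errors: sqrt(1/0.625) = 1.26.

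With AR(1) correlation by visit number (not by calendar week) the ratio is 1.20 at 0.5 and 1.14 at 0.7. The 6-week contrast is therefore 14-26% less precise in standard error. For the average of weeks 2 and 6, the ratios to the four-visit average are 1.10, 0.98 and 0.91 in the same order.

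**False positives if nothing changes** (two-sided 5% assumed). With one contrast in each of four independent constructs, 1 - 0.95^4 = 18.5%. By simulation with between-construct correlation 0.5 it is about 15.5%. This 16-19% is the same whether the single contrast is the four-visit average or week 6. With 16 visit-by-visit tests, simulation gives 38-49% under the same correlation structures, counting any significant visit as a finding.

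**The case for a change.** The strongest argument for a change is that calling an analysis exploratory excuses uncorrected p-values but does not say what is being compared. The results are meant to guide Version 3 of the app, which Study 3 will test. Whether the mechanisms move during encouraged use or only later is useful for that design. Naming the contrast would take a few sentences and need no new data, and it would stop the choice being made after the results are known.

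Part of this stands. The sentence is incomplete, and the range from 4 to 16 tests shows that the choice affects how results look.

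The rest is weaker. A visit-by-visit reading mixes nothing. A contrast statement among visits would ordinarily treat time as a five-level factor, and such a model already estimates a mean at every visit. The plan does not say that only a pooled number will be reported, so fading and late change can be seen from the same fit. Nor do the documents single out week 6 for this aim. The average of weeks 2 and 6, or the six-month average, would serve as well, so fixing on week 6 is a preference that costs precision. Reporting the other visits as secondary would still leave 16 unadjusted comparisons on the page.

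**Conclusion.** The concern does not call for a change. The contrast sentence omits its visits and weights, and equal weighting would put half the weight on the 3- and 6-month surveys. But the mismatch appears only if Aim 2 is confined to the strongly encouraged 7 weeks, and the protocol does not confine it. Either sensible reading, a six-month average or separate visit comparisons, gives a valid description of change over time.

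A week-6 headline is a trade-off. It gives a sharper question at a standard error 14-26% larger, with no gain over a single pooled contrast in the 16-19% chance of a false positive. Those percentages rest on assumed correlations, equal numbers per visit and a 5% level. The dilution figures rest on an assumed r.

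The study's stated main purpose is qualitative input, the analysis is declared exploratory, and no sample size or decision rule depends on Aim 2. The missing detail is one that the analyst must settle to write the model and can settle sensibly.
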